3. INVESTIGATIONAL PLAN

3.1. Overview of Study Design

Study TAS-120-202 is an open-label, multinational, 3-arm, Phase 2 study evaluating the efficacy, safety, tolerability, PK, and pharmacodynamics of futibatinib in patients with *FGFR* aberrations. Eligible patients will be assigned to 1 of 3 treatment cohorts based on diagnosis and *FGFR* gene aberration status (Figure 1):

[figure not shown]

Figure 1: Study Schema

Patients will receive futibatinib at an oral dose of 20 mg once a day on a continuous 28-day cycle.

Treatment will continue until disease progression, unacceptable toxicity, or any other of the criteria for treatment discontinuation is met (Section 4.4). For patients who discontinue treatment for reasons other than disease progression, response assessments should be continued until disease progression is documented or until initiation of subsequent new anticancer therapy (whichever occurs first).

Patients will be followed for survival every 12 weeks (± 2 weeks) until survival events (deaths) have been reported for at least 75% of enrolled patients in each Cohort, the patient withdraws consent, or the study is terminated early by the Sponsor.

Additional cohorts may be added in the future in case of new emerging data. This change will be implemented through a protocol amendment which will describe the rationale for the addition(s).

3.2. Scientific Rationale for Study Design

Please see Section [1.3](#).

3.3. Study Periods and Visits for Each Patient

The study periods / visits described in this section are defined for all patients. Please see the schedule of events for an outline of all assessments to be performed during each study period / visit.

For all patients, the Safety Assessment Period begins at the time informed consent has been documented and continues until at least 30 days after the last dose of futibatinib. After the 30-day Safety Follow-Up Visit (see below), patients who have not started treatment with a new anticancer therapy will be assessed for drug-related serious adverse events (SAEs) only.

For each patient, the Study Duration is defined as the time informed consent has been documented to the last day of Disease Assessment Follow-up / Survival Follow-up (see below).

3.3.1. Screening Period

The Screening Period is defined as the time informed consent has been documented to when they receive the first dose of futibatinib. Determination of eligibility is based on the entry criteria enumerated in Section [4](#). No protocol-specific procedures or assessments may be performed prior to documented consent, except for procedures that represent standard-of-care.

3.3.2. Treatment Period and End of Treatment Visit

Treatment discontinuation may occur for any of the reasons listed in Section [4.4](#). The treatment period is the time from first dose of futibatinib (Day 1) to the date of last dose of futibatinib. An end-of-treatment (EOT) visit must be performed within 7 days after the decision is made to discontinue futibatinib; at this visit, every effort should be made to perform the assessments outlined in the schedule of events. For patients who discontinue at a planned study visit, that visit may be considered the EOT visit if all assessments required at EOT are performed.

3.3.3. Safety Follow-Up Period and 30-Day Safety Follow-Up Visit

The Safety Follow-Up Period is the time from the date of last dose of study drug through the 30-Day Safety Follow-Up Visit, which must be performed 30 days (+7 days) following the last dose of study drug. If the patient starts new anticancer therapy within 30 days of the last dose of study drug, the 30-Day Safety Follow-Up Visit should be performed before the start of new anticancer therapy. Every effort should be made to perform the assessments outlined in the schedule of events. If the patient is unable to return to the study site, a follow-up phone call can

be made by the study site to collect any new safety information that occurred during the Safety Follow-up Period.

After the 30-Day Safety Follow-Up Visit (see below), patients who have not started treatment with a new anticancer therapy will be assessed for drug-related SAEs only.

3.3.4. Post-Discontinuation Considerations

Patients who discontinue without documented disease progression should continue to undergo response assessments according to the Schedule of Events (that is, every 8 weeks \pm 7 days) until progressive disease (PD) is documented, new anticancer therapy is initiated, the study is terminated, or the patient dies, withdraws consent, or is lost to follow-up).

3.3.5. Survival Follow-Up

Once a patient discontinues study treatment, regardless of the reason, Survival Follow-Up will begin, unless the patient withdraws consent or the study is terminated early by the Sponsor. During this period, the patient or family should be contacted for Survival Follow-Up every 12 weeks (\pm 2 weeks) until survival events (deaths) have been reported for 75% of enrolled patients, patient withdraws consent or the study is terminated early by the Sponsor. In addition, all subsequent anticancer treatments will be recorded.

3.4. Study Completion and Study Extension

The study will be considered complete when:

- Survival events (deaths) have been reported for at least 75% of enrolled patients in either Cohort A, B, or C, whichever comes last; or
- The study is halted early for any reason.

Following Study Completion, patients deriving benefit from study drug in the opinion of the Investigator and Sponsor may be permitted to continue treatment with futibatinib in a Study Extension phase. The Sponsor will inform study sites when a Study Extension phase is initiated. During Study Extension, patients may receive treatment until withdrawal criteria are met and study drug is available.

All safety assessments are to be continued according to the Study Extension phase schedule ([Table 3](#)). Specifically, study extension data collection is to include, at a minimum:

- Study drug administration
- Study drug accountability
- Serious adverse events
- Non-serious AEs that are related to study drug or result in treatment discontinuation
- Any cases of pregnancy or overdose

3.5. Patient Enrollment

Eligibility must be verified prior to patient enrollment. Patients will be enrolled via an Interactive Voice/Web Response System (IXRS). The patient should receive the first dose of study drug within 3 days following enrollment.

3.6. End of Trial

The end of the trial will occur when all patients (including patients in the Study Extension phase, if any) have discontinued treatment and undergone all protocol-mandated assessments (including the 30-Day Safety Follow-Up Visit).

4. SELECTION AND WITHDRAWAL OF PATIENTS

Results of *FGFR* gene aberration status should be available before the patient undergoes any protocol-specific procedures. Waivers will not be granted for any of the eligibility criteria.

4.1. Inclusion Criteria

A patient must meet all of the following inclusion criteria to be eligible for participation in this study:

1. Provide documented informed consent (refer to Section [6.3](#))
2. ≥ 18 years of age (or meets the country's regulatory definition for legal adult age, whichever is greater)
3. Eastern Cooperative Oncology Group (ECOG) performance status 0 or 1
4. Has recovered from the acute toxic effects of prior anticancer therapy to baseline or Grade 1 (except toxicities which are not clinically significant such as alopecia)
5. Known *FGFR* aberration status and tumor type that meet all of the criteria for one of the following cohorts:

a. Cohort A

- i. Histologically confirmed, locally advanced, advanced, or metastatic solid tumors harboring a *FGFR1-4* rearrangement determined in tumor tissue using next-generation sequencing (NGS), fluorescence in situ hybridization (FISH), or other assays that can determine gene rearrangements in tumor tissues. Patients with primary brain tumor or iCCA are not eligible.
- ii. Measurable disease per RECIST 1.1
- iii. Had disease progression/recurrence after standard treatment for their advanced or metastatic cancer

b. Cohort B

- i. Histologically confirmed, locally advanced, advanced, or metastatic gastric or GEJ adenocarcinoma harboring a *FGFR2* amplification. The tumor must have an *FGFR2/CEN10* ratio of ≥ 5 or an *FGFR2* copy number ≥ 10 signals per cell determined in tumor tissue using NGS, FISH, or other assays that can determine gene amplifications in tumor tissues.
- ii. Measurable disease per RECIST 1.1
- iii. Received at least 2 prior systemic regimens for advanced/metastatic disease
- iv. Experienced disease progression/recurrence during or after the most recent prior systemic treatment for advanced/metastatic gastric or GEJ cancer.

c. Cohort C

- i. Confirmed MLN with a *FGFR1* rearrangement as defined by WHO criteria
- ii. Not a candidate for hematological stem cell transplant (HSCT) or relapsed after HSCT and donor lymphocyte infusion, and progressed and not a candidate for other therapies.
6. Has archival or fresh tumor tissue (preferably in block format) for Cohorts A and B and bone marrow tissue for Cohort C available to send to central laboratory.

7. Adequate organ function as defined by the following criteria:

a. Cohorts A and B:

- i. Absolute neutrophil count (ANC) $\geq 1.0 \times 10^9/L$
- ii. Platelet count $\geq 75,000/mm^3$ ($\geq 75 \times 10^9/L$)
- iii. Hemoglobin ≥ 9.0 g/dL
- iv. ALT and aspartate aminotransferase (AST) $\leq 3.0 \times$ upper limit of normal (ULN); if liver function abnormalities are due to underlying liver metastasis, AST and ALT $\leq 5.0 \times$ ULN.
- v. Total bilirubin $\leq 1.5 \times$ ULN, or $\leq 3.0 \times$ ULN for patients with Gilbert's syndrome.
- vi. Creatinine clearance (CrCl) (calculated or measured value): ≥ 40 mL/min. For calculated CrCl, use the Cockcroft-Gault formula (Section 6).
- vii. Phosphorus < 1.5 ULN

b. Cohort C

- i. ALT and AST $\leq 3.0 \times$ ULN; if liver function abnormalities are due to underlying liver metastasis, AST and ALT $\leq 5.0 \times$ ULN.
- ii. Total bilirubin $\leq 1.5 \times$ ULN, or $\leq 3.0 \times$ ULN for patients with Gilbert's syndrome.
- iii. CrCl (calculated or measured value): ≥ 40 mL/min. For calculated CrCl, use the Cockcroft-Gault formula (Section 6).
- iv. Phosphorus < 1.5 ULN

8. Women of child-bearing potential (WOCBP) must have a negative serum pregnancy test prior to administration of the first dose of futibatinib. Female patients are not considered to be of child-bearing potential if they are post-menopausal (no menses for 12 months without an alternative medical cause) or permanently sterile (hysterectomy, bilateral salpingectomy, or bilateral oophorectomy).
9. Both males and females of reproductive potential must agree to use effective birth control during the study prior to the first dose and for 90 days after the last dose or longer based on local requirements.
10. Ability to take medications orally (feeding tube is not permitted).
11. Willing and able to comply with scheduled visits and study procedures.

4.2. Exclusion Criteria

A patient must not meet any of the following exclusion criteria to be eligible for participation in this study:

1. Currently receiving an investigational drug in a clinical trial or participating in any other type of medical research judged not to be scientifically or medically compatible with this study. If a patient is currently enrolled in a clinical trial involving non-approved use of a device, then agreement with the Investigator and the Sponsor's Medical monitor is required to establish eligibility.

2. History and/or current evidence of any of the following disorders:
 - a. Non-tumor related alteration of the calcium-phosphorus homeostasis that is considered clinically significant in the opinion of the Investigator.
 - b. Ectopic mineralization/calcification, including but not limited to soft tissue, kidneys, intestine, or myocardia and lung, considered clinically significant in the opinion of the Investigator.
 - c. Retinal or corneal disorder confirmed by retinal/corneal examination and considered clinically significant in the opinion of the Investigator.
3. Corrected QT interval using Fridericia's formula (QTcF) >470 msec. Patients with an atrioventricular pacemaker or other condition (for example, right bundle branch block) that renders the QT measurement invalid are an exception and the criterion does not apply.
4. Treatment with any of the following within the specified time frame prior to the first dose of futibatinib:
 - a. Major surgery within 4 weeks (surgical incision should be fully healed)
 - b. Radiotherapy for extended field within 4 weeks or limited field radiotherapy within 2 weeks
 - c. A drug that has not received regulatory approval for any indication within 14 or 21 days of treatment for a nonmyelosuppressive or myelosuppressive agent, respectively
5. Received strong inhibitors or inducers of CYP3A4 within 2 weeks
6. Prior treatment with an FGFR inhibitor
7. A serious illness or medical condition(s) including, but not limited to, the following:
 - a. Known acute systemic infection
 - b. Myocardial infarction, severe/unstable angina, or symptomatic congestive heart failure within the previous 6 months
 - c. History or current evidence of uncontrolled ventricular arrhythmia
 - d. Chronic diarrhea diseases considered to be clinically significant in the opinion of the Investigator
 - e. Congenital long QT syndrome, or any known history of torsade de pointes, or family history of unexplained sudden death
 - f. Other severe acute or chronic medical or psychiatric condition or laboratory abnormality that may increase the risk associated with study participation or futibatinib administration, or may interfere with the interpretation of study results, and in the judgment of the Investigator would make the patient inappropriate for entry into this study
8. Active central nervous system (CNS) metastasis and/or carcinomatous meningitis. Patients with previously treated brain metastases that are clinically and radiologically stable (for at least 4 weeks prior to enrollment) are eligible.

9. Known additional malignancy that is progressing or has required active treatment within the past 2 years. Patients with basal cell carcinoma of the skin, squamous cell carcinoma of the skin, or carcinoma in situ (eg, breast carcinoma, cervical cancer in situ) that have undergone potentially curative therapy are not excluded.
10. Pregnant or breastfeeding.

4.3. Screen Failure

Screen failures are defined as patients who consent to participate in the clinical study but are not subsequently enrolled in the study. A minimal set of screen failure information is required to ensure transparent reporting of screen failure patients to respond to queries from regulatory authorities. Minimal information includes demography, screen failure details, eligibility criteria, and any SAE after completion of the ICF.

Patients who do not meet the criteria for participation in this study (screen failure) may be rescreened a maximum of 3 times. Rescreened patients should be assigned the same patient identification code as for the initial screening.

4.4. Discontinuation of Treatment

A patient will be discontinued from all study drug for any of the following reasons:

1. Disease progression
2. Unacceptable AEs, or change in underlying condition such that the patient can no longer tolerate therapy, as evidenced by a dose delay >28 days from the scheduled start date of the next cycle or need for more than 2 dose reductions outlined in this protocol
3. Physician's decision, including need for other anticancer therapy not specified in the protocol or surgery or radiotherapy to the only site(s) of disease being followed in the study
4. Pregnancy
5. Termination of the study by the Sponsor
6. At the patient's request at any time irrespective of the reason

Patients who withdraw consent for further treatment may choose to remain on study; in such a case, all study evaluations should continue as outlined in this protocol. If the patient withdraws consent to all follow-up assessments, the patient should be considered to have discontinued the study as described in Section 4.5.

4.5. Withdrawal from the Study

A patient will be withdrawn from all study interventions and assessments (that is, discontinued from the study without follow-up) for any of the following reasons:

1. Death
2. Lost to follow-up

- A patient will be considered lost to follow-up if he or she repeatedly fails to return for scheduled visits and is unable to be contacted by the study site.
- The following actions must be taken if a patient fails to return to the clinic for a required study visit:
 - The site must attempt to contact the patient and reschedule the missed visit as soon as possible and counsel the patient on the importance of maintaining the assigned visit schedule and ascertain whether or not the patient wishes to and/or should continue in the study.
 - Before a patient is deemed lost to follow-up, the Investigator or designee must make every effort to regain contact with the patient (where possible, 3 telephone calls and, if necessary, a certified letter to the patient's last known mailing address or local equivalent methods). These contact attempts should be documented in the patient's medical record.
 - Should the patient continue to be unreachable, they will be considered to have withdrawn from the study.

3. Patient withdrawal of consent to further follow-up assessments, irrespective of the reason.

5. STUDY TREATMENT

5.1. Study Drug Administration

A study cycle is defined as 28 days. Futibatinib is supplied as 4 mg tablets and will be taken orally at a dose of 20 mg daily until the patient meets any of the administration discontinuation criteria (see Section 4.4).

Futibatinib should be administered under fasting conditions. It should be taken with a glass of water, on an empty stomach, at the same time each day. No food should be consumed for 2 hours prior and 1 hour after the dose of futibatinib, but patients may drink water during this period.

When a PK sample is collected, futibatinib should be administered on site after collection of the first PK sample.

In the event of a dosing delay up to 12 hours after the scheduled dosing time, the patient should still take that day's dose. If the dosing delay continues for >12 hours after the scheduled dosing time, or if the patient vomits after a dose, the patient should skip dosing for that day and not make up for it the following day.

5.2. Dose and Schedule Modifications

Stepwise dose reductions of 4 mg to 16 mg (first reduction) and 12 mg (second reduction) are permitted based on toxicities. If dose reduction fails to result in achieving the minimal criteria to resume treatment or, if toxicities occur which would necessitate reduction of the dose of futibatinib below 12 mg QD, the patient should be discontinued from futibatinib.

Following a dose reduction, if a benefit/risk assessment favors an increase of futibatinib dose up to the initial starting dose (20 mg QD), an agreement with the Sponsor's Medical monitor is required prior to the dose increase.

If toxicities related to the dose reduction do not recover based on the criteria defined below within 28 days after the last dose of futibatinib, the patient will be discontinued permanently from treatment (Section 4.4). If resumption criteria are met within 28 days of the last dose of futibatinib, the patient may resume futibatinib treatment at the appropriate dose level.

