Grade 1	
If there is no evidence of ocular toxicity on ophthalmologic examination, continue futibatinib therapy at the same dose level.
 
If diagnosis from ophthalmologic examination is keratitis or retinal abnormality such as central serous retinopathy (CSR)/ retinal pigment epithelial detachments (RPED), withhold futibatinib until signs and symptoms have resolved.
 
If toxicity is reversible (complete resolution or stabilization and asymptomatic) in 4 weeks according to ophthalmologic examination, resume futibatinib therapy at the next lower dose level after consultation with the Sponsor's Medical monitor.
 
Monitor for recurrence every 1 to 2 weeks for a month and as clinically appropriate thereafter. If there is no recurrence then re-escalation can be considered in consultation with the Sponsor's Medical monitor.

Grade 2	
Withhold futibatinib therapy.
 
If there is no evidence of drug-related corneal or retinal pathology on ophthalmologic examination, withhold futibatinib until signs and symptoms have resolved. Resume futibatinib therapy at the next lower dose level.
 
If diagnosis from ophthalmologic examination is keratitis or retinal abnormality, withhold futibatinib until signs and symptoms have resolved or stabilized.
 
If toxicity is Grade 2 and reversible (complete resolution or stabilization and asymptomatic) within 4 weeks according to ophthalmologic examination, resume futibatinib therapy at the next lower dose level after consultation with the Sponsor's Medical monitor.
 
Monitor for recurrence every 1 to 2 weeks for a month and as clinically appropriate thereafter. If there is no recurrence then re-escalation can be considered in consultation with the Sponsor's Medical monitor.

Grade 3	
If the toxicity is Grade 3, report as an SAE and consider permanent discontinuation of futibatinib. If the toxicity is Grade 3 and reversible (complete resolution or stabilization and asymptomatic) within 4 weeks and the patient is receiving clinical benefit, and the Investigator and the Sponsor's Medical monitor agree that re-starting drug is in the best interest of the patient, then futibatinib therapy may be resumed at 2 dose levels lower if appropriate. Monitor for recurrence using appropriate investigations every 1 to 2 weeks for a month and as clinically appropriate thereafter.
 
For cases of recurrence, consider permanent discontinuation.

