7.0 < P ≤10.0 (mg/dL) 2.26< P ≤3.23 (mmol/L)	Dose reduce futibatinib to the next lower dose level and intensify phosphate-lowering therapy. Reassess serum phosphate within 7 days and at least once a week. If the serum phosphorus level has resolved to ≤5.5 mg/dL/1.78 mmol/L within 14 days after dose reduction, continue futibatinib at the reduced dose level. If the serum phosphorus level has not resolved to ≤5.5 mg/dL/1.78 mmol/L after 14 days, further reduce futibatinib from the last reduced dose level (or no lower than 12 mg QD). If the serum phosphorus level has not resolved to ≤5.5 mg/dL/1.78 mmol/L after 14 days of the second dose reduction of futibatinib (or no lower than 12 mg QD), interrupt dosing with futibatinib until it is resolved to ≤5.5 mg/dL/1.78 mmol/L before resuming futibatinib at the reduced dose prior to dose interruption.
P >10.0 (mg/dL) P >3.23 (mmol/L)	Interrupt futibatinib until serum phosphate has resolved to ≤5.5 mg/dL/1.78 mmol/L, then resume futibatinib at the next lower dose level and intensify phosphate-lowering therapy. Reassess serum phosphate within 7 days and at least once a week. If after 2 dose interruptions and 2 dose reductions the serum phosphorus level has not resolved to ≤5.5 mg/dL/1.78 mmol/L after 14 days, permanently discontinue futibatinib.

Abbreviations: P=phosphorus; QD=once a day; TID=three times a day; ULN=upper limit of normal

^a Serum phosphorus will be tested 4 days (± 24 hours) after Day 1 of Cycle 1 to initiate early intervention for hyperphosphatemia if indicated.

^b mmol/L=mg/dL x 0.3229 (conversion factor).

^c Interrupt futibatinib if any toxicities are intolerable. If or when the toxicity resolves to a tolerable state, consideration can be given to resuming futibatinib at the same dose if deemed appropriate or reduced by one dose level if needed.

^d Serum calcium levels should be assessed at the same time.

^e Futibatinib will be permanently discontinued if ectopic mineralization or calcification associated with hyperphosphatemia and considered clinically significant are observed.

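### The permanent-stop rules for dose reductions (a count in 4.4, a 12 mg floor in 5.2) do not fit the re-escalation rule, the two-level step in Table 7 or the top row of Table 8

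*Protocol*

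**What the plan says.** All references are to the current Amendment 2 text.

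- **Starting dose (Protocol 5.1).** Futibatinib "will be taken orally at a dose of 20 mg daily".
- **Ladder (5.2).** "Stepwise dose reductions of 4 mg to 16 mg (first reduction) and 12 mg (second reduction) are permitted based on toxicities".
- **Floor (5.2).** "if toxicities occur which would necessitate reduction of the dose of futibatinib below 12 mg QD, the patient should be discontinued from futibatinib". The same sentence has a second trigger: "If dose reduction fails to result in achieving the minimal criteria to resume treatment".
- **Count (4.4).** A patient comes off study drug for intolerable toxicity shown by, among other things, "need for more than 2 dose reductions outlined in this protocol".
- **Re-escalation.** Section 5.2 allows the dose to go back up, as far as 20 mg, if the Medical monitor agrees. Table 7, Grades 1 and 2, allows it in consultation with the monitor when there is no recurrence.
- **Table 7, Grade 3 ocular toxicity.** If the event reverses within 4 weeks and the Investigator and monitor agree, "then futibatinib therapy may be resumed at 2 dose levels lower if appropriate". Footnote a allows re-treatment one or two levels down. Neither repeats the 12 mg floor.
- **Table 8, phosphorus above 7.0 and up to 10.0 mg/dL.** The second reduction is capped at 12 mg. If phosphorus is still unresolved 14 days later, dosing is held until it resolves, "before resuming futibatinib at the reduced dose prior to dose interruption".
- **Table 8, phosphorus above 10.0 mg/dL.** Hold, then restart one level lower. No floor is given. The row has its own stop test: two interruptions, two reductions and no resolution after 14 days.

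**The concern.** Permanent discontinuation and the lowest dose given should have one answer for each patient. Here one section limits the number of reductions and another limits the dose, while three further passages allow moves that were not fitted to either limit. Two sites, or one site reading two pages, could handle identical patients differently.

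At stake are whether anyone is treated below 12 mg, whether a patient who is benefiting is taken off drug, and how consistently the resulting data can be read. SAP 5.6.1.2 and 5.6.2.3 summarise dose reductions, discontinuations and the adverse events that lead to discontinuation. In a single-arm study there is no comparator to absorb inconsistent handling. The phosphorus rows are unlikely to be rarely used: Protocol 1.2.1 lists hyperphosphatemia first among the events seen in more than 20% of patients at 20 mg daily.

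**Working it through.** **Inputs.** Start 20 mg (5.1), steps of 4 mg (5.2), floor 12 mg (5.2), limit of two reductions (4.4).

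**The plan's own ladder.** The dose after k single-level, unreversed reductions is 20 − 4k:

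- k = 1: 16 mg
- k = 2: 12 mg
- k = 3: 8 mg
- k = 4: 4 mg

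This reproduces the 16 and 12 mg in 5.2. On such a path k > 2 holds exactly when 20 − 4k < 12, so 4.4 and 5.2 are the same rule.

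**Other permitted moves.** For each path, count the reduction events (4.4 stops if more than 2) and find the lowest dose (5.2 stops if below 12 mg).

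| Path (mg) | Source of the move | Events | Lowest dose | 4.4, counting events | 5.2 floor |
|---|---|---|---|---|---|
| 20-16-20-16-12 | re-escalation | 3 | 12 | stop | no stop |
| 20-16-12-16-12 | re-escalation | 3 | 12 | stop | no stop |
| 20-16-8 | Table 7 Grade 3 from 16 mg | 2 | 8 | no stop | stop |
| 20-16-12-8 | Table 8, above 10.0, from 12 mg | 3 | 8 | stop | stop |
| 20-12-8 | two-level drop, then Table 8, above 10.0 | 2 | 8 | no stop | stop |

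**(a) Re-escalation.** The first two rows split the two rules. The split depends on the counting unit. If 4.4 means net levels below 20 mg, the count at 12 mg is (20 − 12)/4 = 2 and the patient continues. If it means events, the count is 3 and the patient stops. No passage says which.

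**(b) Table 7.** Two levels below 16 mg is 16 − 2×4 = 8 mg, and two levels below 12 mg is 4 mg. Only from 20 mg does the step stay on the ladder, at 12 mg. From 16 mg the table allows resumption at a dose at which 5.2 discontinues.

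**(c) Table 8, above 10.0.** From 12 mg the next lower level is 12 − 4 = 8 mg. Section 5.2 discontinues, and so does 4.4 if two reductions have already been used. The row restarts lower and stops only on its own three-part test.

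Points (b) and (c) do not depend on how 4.4 is counted. On the net-level reading, (20 − d)/4 > 2 is the same condition as d < 12 for any dose d. Sections 4.4 and 5.2 then agree, and the tables still go below the floor.

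**Softer point: Table 8, 7.0 to 10.0.** This row respects 12 mg. Its last step holds and resumes at 12 mg after reductions have failed to bring phosphorus down, whereas 5.2 discontinues when dose reduction does not achieve the criteria to resume. The two can be squared if a hold that achieves resolution counts as meeting those criteria, but the text does not say so.

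**The case against.** The best defence is that there is one rule, stated twice. Section 5.2 names its reductions by dose, 16 mg first and 12 mg second, so more than two of the reductions outlined in the protocol can be read as going below 12 mg. Sections 4.4 and 5.2 are also alternative triggers: meeting either is enough, 5.1 sends the reader to 4.4, and 5.2 nowhere orders anyone to continue. The tables sit under 5.2, so its floor could be taken to cap them. Table 7 is permissive, and the protocol describes Table 8 as suggested guidance. Section 5.2 re-escalation, the Table 7 Grade 3 restart and footnote a all need the Medical monitor's agreement, so a site does not act alone.

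Much of this stands and limits the weight of the point. It does not close the gap. The net-level reading is available but not written down. No passage ranks 5.2 above the tables, and Table 8 repeats the floor in one row only, which invites the inference that the other row has none. The Table 8 rows do not call for the monitor's agreement.

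Three stronger readings are tempting but not supported:

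- **A single drop from 20 to 12 mg puts 4.4 and 5.2 in conflict.** It does not. Both let the patient continue, and if a further reduction is needed, 5.2 alone is enough to stop.
- **Any patient at 12 mg with phosphorus above 7.0 is caught between the rules.** The 7.0 to 10.0 row asks for no third reduction, since it caps the dose and then holds. Values above 10.0 belong to a different row.
- **Hold and restart at 12 mg is unlimited.** The number of holds is not capped, but the 28-day recovery limit in 5.2 applies to each one, and Table 8 footnote e stops treatment for clinically significant mineralization or calcification.

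**Conclusion.** The point holds in three places: the uncounted status of reversed reductions, the two-level step in Table 7 without a floor, and the top row of Table 8 without a floor. The 7.0 to 10.0 row is an uneasy fit with 5.2, not a clear breach.

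Point (a) rests on 4.4 being read as a count of events and disappears on a net-level reading. Points (b) and (c) assume only that a level is 4 mg, as 5.2 states, and that the tables mean what they say at 16 and 12 mg.

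The size is modest. The documents give no basis for estimating how many patients would meet these paths, and no sample-size, power or error-rate figure is touched. It is still worth correcting, because these rules decide permanent discontinuation and the lowest dose given. Which rule is clinically right is outside this review.

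**What to change.** Reconcile Protocol 4.4, 5.2, Table 7 (Grade 3 row and footnote a) and both upper rows of Table 8 (7.0 to 10.0 and above 10.0) to one stop criterion. The clarification should state:

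- whether the limit is the number of reduction events or the dose level;
- whether a reduction that was later reversed still counts;
- how a two-level step counts;
- which passage takes precedence for a patient at 16 mg or 12 mg under Table 7 or Table 8;
- how the hold and restart in the 7.0 to 10.0 row relates to the failed-reduction clause in 5.2.

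The content of the rule is for the sponsor's clinical team. The cost is a few lines in a protocol clarification, with no extra visits or patients.
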